### 4.2.3 Survival

Survival rates over time will be estimated from the Kaplan-Meier curve for time to death based on the Safety set.

### 4.3 Growth parameters

Growth parameters comprise length for age, weight for age, weight for length, head circumference for age, chest circumference, head to chest circumference ratio, and arm circumference are to be assessed through the study.

The WHO child growth standards (WHO Child Growth Standards, 2006) will be used to determine the percentiles for each parameter. The WHO provides a SAS macro (SAS igrowup package) which can be downloaded from a website [WHO Anthro] and this will be utilized to calculate the percentiles for each child.

The change from baseline to each windowed analysis visit will be summarized using descriptive statistics for the following growth parameters: weight for age, weight for length/height, head circumference, chest circumference, head to chest circumference ration and arm circumference. Presentations will be made for all groups.

Two additional analyses will be performed examining the change between WHO percentiles (Sproule 2012). In the first analysis, subjects with weight below the 5th percentile based on WHO growth charts, in the second, subjects with decreased growth velocity resulting in falling more than major percentiles (3rd, 5th, 10th, 25th, 50th, 75th, 90th, 95th, 97th) over a 6-month period will be used. Both analyses will be presented by windowed analysis visit by index treatment group and overall.

Growth parameters will also be summarized by age of SMA onset ( $\leq 6$  months,  $>6$  months).

#### *Missing values*

No imputation will be performed for missing data.

### 4.4 Number of Hospitalizations

The number and reason for hospitalizations per subject will be summarized.

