¹ A blood sample will be collected at Screening for *SMN2* copy number only from those subjects without genetic documentation of *SMN2* copy number. For all other subjects, a blood sample will be collected at any time during the study for analysis of *SMN2* copy number by the central laboratory.

² After the injection of study treatment or sham procedure on Day 1, subjects will remain at the study site for at least 24 hours (Day 2) for safety monitoring. On the day following the injection of study treatment or sham procedure on Days 15, 29, 64, 183, and 302, there will be safety monitoring through telephone contact. During that telephone contact (i.e., Days 16, 30, 65, 184 and 303), changes in concomitant medications and AEs, information on the subject’s daily ventilator/Bi-PAP use, and health status will be recorded.

³ End of Part 1 is one of the following: Part 1 Final Follow-up Evaluation (Day 422 [±7 days]) according to the study schedule, early Part 1 Final Follow-up Evaluation to allow for rollover into Part 2, or Early Termination Evaluation for subjects who withdraw from the study during Part 1.

⁴ For subjects not transitioning into Part 2, the date of the End of Part 1 Evaluation assessments will be the end of study. For subjects who transition to Part 2, the date of the End of Part 1 will be the date of first dose in Part 2.

⁵ At the End of Part 1 evaluation, in order to allow transition to Part 2, subjects will be unblinded.

⁶ Vital signs include resting systolic and diastolic blood pressure, pulse rate, respiratory rate, temperature, pulse oximetry, and transcutaneous carbon dioxide. Pulse oximetry and transcutaneous carbon dioxide will be measured predose at each evaluation. For subjects who are not receiving noninvasive ventilation, pulse oximetry will be measured overnight once a week at home.

⁷ Vital signs (resting systolic and diastolic blood pressure, pulse rate, respiratory rate, temperature, and pulse oximetry) will be collected at 4 timepoints: 1, 2, 4, and 6 hours (all ±15 minutes) after the injection of study treatment.

⁸ Vital signs (resting systolic and diastolic blood pressure, pulse rate, respiratory rate, temperature, and pulse oximetry) will be collected within 20 to 24 hours after the injection of study treatment or sham procedure.

CONFIDENTIAL

The information contained herein may not be used, disclosed, or published without the written consent of Biogen MA Inc.

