- ⁹ At the evaluations scheduled for injection of study treatment or sham procedure, subjects will be assessed for the following growth parameters: body length, head circumference, chest circumference, and arm circumference.
- ¹⁰ Neurological examinations include assessment of mental status, level of consciousness, sensory function, motor function, cranial nerve function, and reflexes.
- ¹¹ Neurological examinations will occur between 4 to 6 hours after the injection of study treatment or sham procedure.
- ¹² Blood chemistry, hematology, and urinalysis panels.
- ¹³ Samples for safety laboratory tests will be collected before the injection of study treatment or sham procedure on Days 64 and 183 only.
- ¹⁴ End of Part 1 safety laboratory tests may be performed locally in addition to centrally to accommodate the Part 2 Day 1 dosing.
- ¹⁵ Refer to [Table 5](#) for CSF PK sample schedule. The CSF samples will be analyzed for Nusinersen concentrations. The remaining CSF sample will be stored for optional future biomarker analyses.
- ¹⁶ Blood samples for PK assessment will be collected 4 hours (± 1 hour) after the injection of study treatment or sham procedure only on Day 1. Refer to [Table 5](#) for the plasma PK sample schedule.
- ¹⁷ Blood samples for PK assessment will be collected before the injection of study treatment or sham procedure on Days 64 and 183 only. Refer to [Table 5](#) for the plasma PK sample schedule.
- ¹⁸ Overnight stay (at least 24 hours) is required after the first injection of study treatment or sham procedure. Following all subsequent injections or sham procedures, a stay of at least 6 hours at the study site is required; overnight stays are optional on these days.
- ¹⁹ In addition to concomitant medications, ancillary procedures will be recorded.
- ²⁰ AEs and SAEs will be collected in the case report form from the time of signing of the informed consent form as described in [Section 15.3.1](#) and [Section 15.3.2](#).

CONFIDENTIAL

The information contained herein may not be used, disclosed, or published without the written consent of Biogen MA Inc.

4.2.2. Schedule of Events: Part 2

Table 3: Part 2 Schedule of Activities for Subjects Randomized to Receive Nusinersen in Part 1

Study Period	Part 2 Treatment/Follow-Up									
	Study Day	Day 1			Day 2 ¹	Days 120, 239, 358, 477, 596, 715 (± 7 days) ²			Days 121, 240, 359, 478, 597, 716 ¹	Part 2 Final Follow-Up (Day 835 [± 7 days]) ³ or Part 2 Early Termination ⁴

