## **2 Statistical Methods: General Considerations**

In this SAP, the terms “control” and “previous control” refer to the set of subjects who were randomized to undergo the sham procedure during the Part 1.

In order to distinguish nominal visit names from duration defined in days, visit names will be referred to as “Day 15”, “Day 29”, etc., and “15 days” or “29 days” etc. will be used to define time intervals.

Due to emergent data from the Nusinersen clinical development program, the subjects in Part 1 ended the study early as follows: subjects randomized to sham terminated Part 1 first irrespective of Part 1 planned dosing days and subjects randomized to Nusinersen transitioned to Part 2 accordingly to their specific dose schedule. Part 2 was also terminated early to allow subjects to

enter the ISIS 396443-CS11 study. For these reasons, the actual study day associated with visits Part 1 and Part 2 will vary widely amongst subjects. Therefore, a windowing schema will be implemented for by visit analyses (see [section 4.1](#))

The safety population will include all subjects who are randomized and receive at least 1 dose of study treatment or sham procedure. Subjects randomized to receive sham procedure but incorrectly treated with Nusinersen will be counted in the ISIS 396443 group from the first dose of Nusinersen received.

The Efficacy set at each visit will be defined as the subset of subjects in the Safety set who has had the opportunity to be assessed at that visit (actual visit for Part 2 or windowed visit for integrated analysis see [section 4.1](#))

The PK population will include all subjects who are randomized and have at least 1 evaluable post dose or post sham-procedure PK sample.

The immunogenicity population will include all subjects who are randomized and have at least 1 evaluable post dose or post sham-procedure immunogenicity data.

For all time-to-event endpoints, (e.g., time to death or permanent ventilation), the date of first dose/sham administration will be used as the reference time point. If the date of first dose/sham procedure is incomplete, the date of randomization will be used.

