Summary statistics will be presented throughout. For continuous endpoints, summary statistics will generally include number of subjects with data, mean, standard deviation, median, minimum and maximum. The mean changes from baseline will be estimated with 95% confidence intervals. For categorical endpoints, summary statistics will generally include: number of subjects dosed, number of subjects with data, and the percentage of those with data in each category. Frequency distributions will be presented as appropriate.

The statistical software, SAS® version 9.4 or above, will be used for all summaries and statistical analyses.

For Part 2, a limited number of summaries will be produced. The approach will be to preserve the Part 1 study groupings as follows for Safety and Efficacy population:

- Previous control.
- Previous ISIS 396443.
- Total (previous control and previous ISIS 396443).

For the integrated analyses, the Safety displays will be grouped as follows:

- Previous control, Part 1, from their first sham procedure in Part 1.
- Previous control, Part 2, from their first ISIS 396443 dose in Part 2.
- Previous ISIS 396443, Part 1 and 2, from their first ISIS 396443 dose in Part 1.
- Total (Previous control Part 2 and previous ISIS 396443 Part 1 and 2)

For the integrated analyses, the Efficacy displays will be grouped as follows:

- Previous control, Part 1, from their first sham procedure in Part 1.
- Previous control, Part 2, from their first ISIS 396443 dose in Part 2.
- Previous control, Part 1 and 2, from their first sham procedure in Part 1.
- Previous ISIS 396443, Part 1 and 2, from their first ISIS 396443 dose in Part 1.

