#### 4.2.1 Change in Ventilator use

In the statistical analysis of Part 1, for each subject the mean number of hours of ventilator was calculated amongst the periods. These periods were created from the first dose of Nusinersen or sham procedure to the nominal visit. (example Day 1: > from Day 1 to Day 15 visit; Day 15: from Day 15 inclusive to Day 29 visit). In Part 2 for each subject the mean number of hours will be calculated for a monthly interval (30 days) starting from the first dose of Nusinersen or sham procedure. The intervals will be: month 1 from Day 1 inclusive to Day 30, Month 2 from Day 30 inclusive to Day 60, and so on.

The change from baseline over time will be presented and a plot of both total and change from baseline will be presented.

For each subject, the total number of hours of ventilation support required during the study will be calculated and prorated according to number of days on study. The percentage of time on ventilator support in total and by type either invasive prophylactic, invasive treatment, or non-invasive prophylactic and not invasive treatment will be presented.

The different respiratory aids/therapies used will be listed

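### Hospitalisations are counted per subject with no allowance for time on study, although the sham column covers Part 1 only and the nusinersen column Parts 1 and 2 (planned 421 against 1255 days)

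*SAP*

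**What the plan says.** SAP 4.4 reads, in full: "The number and reason for hospitalizations per subject will be summarized". It names no display groups, no denominator and no cut-off day. Hospitalisation is not a listed endpoint in Protocol 6.1 to 6.3 or in the SAP's objectives, so no method is given elsewhere.

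SAP 2 sets four columns for the integrated efficacy displays. Three matter most here:

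- the nusinersen column: "Previous ISIS 396443, Part 1 and 2, from their first ISIS 396443 dose in Part 1"
- the sham column: "Previous control, Part 1, from their first sham procedure in Part 1"
- the longer control column: "Previous control, Part 1 and 2, from their first sham procedure in Part 1"

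The fourth is previous control in Part 2, counted from the first nusinersen dose.

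On follow-up, SAP 2 records that "subjects randomized to sham terminated Part 1 first irrespective of Part 1 planned dosing days", that Part 2 was also ended early, and that actual study days differ greatly between subjects. No actual follow-up by group is given.

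For ventilation hours, another quantity that accumulates with time, SAP 4.2.1 does adjust: "the total number of hours of ventilation support required during the study will be calculated and prorated according to number of days on study". SAP 3.3 defines overall time on study and summarises it for Part 2 and for the integrated data, but does not link it to hospitalisations.

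**The concern.** Admissions are recurrent, so a count per child keeps growing for as long as the child is followed. If the efficacy columns of SAP 2 are applied to SAP 4.4, children observed on sham for Part 1 alone stand beside children observed on nusinersen for both parts. The counts would then differ between columns even if admission rates were identical. Within a column, counts from children with very different follow-up are not comparable either.

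At stake is whether the hospitalisation table can be read at all as a comparison with sham. The contrast within the previous-control children has the same problem: their Part 2 count accrues over a longer planned window than their Part 1 count.

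**Working it through.** **1. Inputs.** Part 1 ends at the "Part 1 Final Follow-up Evaluation (Day 422 [±7 days]) according to the study schedule" (Protocol Table 2, footnote 3). Part 2 final follow-up is Day 835 for previous nusinersen (Protocol Table 3) and Day 897 for previous control (SAP 1.4, Part 2 schedule for the sham group). Each part starts on its own Day 1; Part 2 Day 1 is taken to coincide with the end of Part 1.

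**2. The plan's own durations reproduce.** Screening plus Part 1: 28 + 422 = 450 days, as stated in Protocol 7.2. Total: 15 + 28 = 43 months, as stated. By schedule days the total is 28 + 421 + 834 = 1283 days (42.2 months) for nusinersen and 28 + 421 + 896 = 1345 days (44.2 months) for control. Both agree with a stated total of approximately 43 months.

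**3. Planned days per column.** Elapsed days are the final day minus 1. With a common constant rate r, expected admissions per child are r × days/365.25, so the ratio of counts is the ratio of days whatever r is. No admission rate is given in the documents; r = 1 per child-year is assumed below for illustration.

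| Column | Planned days | Expected admissions per child at r = 1 | Nusinersen count ÷ this column |
|---|---|---|---|
| Control, Part 1 (sham) | 422 − 1 = 421 | 1.15 | 1255/421 = 2.98 |
| Control, Part 2 | 897 − 1 = 896 | 2.45 | 1255/896 = 1.40 |
| Control, Parts 1 and 2 | 421 + 896 = 1317 | 3.61 | 1255/1317 = 0.95 |
| Nusinersen, Parts 1 and 2 | 421 + 834 = 1255 | 3.44 | – |

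At r = 0.5 or 2 the expected counts halve or double and the ratios do not move. The SAP 3.3 formula adds one day to each span, which makes no practical difference.

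**4. Composition of the longer control column.** 896/1317 = 68% of its planned time is on nusinersen. Control Part 1 is therefore the only column made up of sham exposure.

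**5. Switch within the control children.** At a constant rate, Part 2 would show 896/421 = 2.13 times as many admissions as Part 1.

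**6. Early termination.** Actual follow-up is not stated, so a range has to be assumed. For sham Part 1, take 183, 302 or 422 days (scheduled visit days). For nusinersen Parts 1 and 2, take 659 to 1198 days (a scheduled day and the upper bound of the last analysis window in SAP 4.1).

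- Sham 422 days: 659/422 = 1.56 to 1198/422 = 2.84
- Sham 302 days: 659/302 = 2.18 to 1198/302 = 3.97
- Sham 183 days: 659/183 = 3.60 to 1198/183 = 6.55

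The null ratio against sham Part 1 therefore runs from about 1.6 to 6.5 and stays above 1 throughout. A shorter sham Part 1 raises it; a shorter Part 2 lowers it.

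**7. After adjustment.** Dividing each count by its own child-years gives a ratio of 1.00 in every column at equal rates.

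**The case against.** The strongest answer is that the efficacy displays include a control column with nearly the same planned follow-up as nusinersen: Parts 1 and 2, 1317 against 1255 days. Suppose the rate is 1 per child-year on sham and 0.5 on nusinersen. That column then shows 1.15 + 0.5 × 2.45 = 2.38 admissions per child against 0.5 × 3.44 = 1.72 on nusinersen. This is 28% fewer in the group treated from the start, which is the right direction. It is a fair point, and it rules out saying that the table as a whole must make nusinersen look worse. It does not supply a sham comparison, because 68% of that column is nusinersen time. In the same scenario the only sham column shows 1.15 against 1.72, a ratio of 1.5 in the wrong direction.

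Two stronger readings are tempting. A reader might infer that nusinersen children were in fact followed three times as long as sham children. The documents do not support this: 2.98 is the ratio on the planned schedule, and both parts stopped early. A reader might also infer that the table will show a threefold excess and so present the drug as harmful. SAP 4.4 specifies no columns, no means and no contrast. Applying the SAP 2 columns is a reasonable inference from where 4.4 sits, not something the plan states, and the factor concerns one column of four.

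It can also be said that time on study is tabulated (SAP 3.3), that treatment-emergent serious adverse events are split into 3-month onset intervals (SAP 5.1.3), and that Part 1 has its own analysis plan, which is not available here. The first lets a reader derive a crude rate by hand. The second covers serious events, not admissions as such. The third may contain a Part 1 comparison. None of them corrects the counts in this table.

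Finally, hospitalisation is not a listed endpoint and the analysis is descriptive. That limits the importance of the point and argues against anything elaborate, but not against a denominator.

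**Conclusion.** The point stands in this form. The planned summary is a recurrent-event count with no time denominator, set by the general column rules beside columns of unequal length. On the planned schedule, equal rates would give a nusinersen count about 3.0 times that of sham Part 1, 1.4 times that of control Part 2 and 0.95 times that of control Parts 1 and 2. The actual figures are unknown; against sham Part 1 they lie between about 1.6 and 6.5 under the follow-up assumed above.

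These sizes assume a constant, common admission rate, the SAP 2 efficacy columns, and Part 2 starting when Part 1 ends. The ratios do not depend on the level of the rate. A change is worth making because the comparison with sham cannot be read from raw counts and the SAP already applies the needed adjustment to ventilation hours.

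**What to change.** In SAP 4.4, name the display columns and report for each one the total admissions, the total child-years and the admissions per child-year. Take child-years from time on study as defined in SAP 3.3, but end sham time at the first nusinersen dose; without that split, a previous-control child's time runs through both parts. Add the same rate restricted to the Part 1 period for both randomised groups. It should be a rate there too, because sham subjects left Part 1 first.

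State whether protocol-required dosing stays are excluded. Protocol 7.2.2 requires at least 24 hours on site after the first procedure, and Protocol 15.1.2 counts an admission of more than 24 hours as a hospitalisation. Previous-control children have that stay at the start of each part; nusinersen children have it once.

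The cost is a few sentences in SAP 4.4 and three extra lines in the table, using admission counts and dates on study that the plan already relies on. No model is needed: with 7 sham children planned, the sham column holds about 7 × 421/365.25 = 8.1 child-years, too little to support one. Days in hospital should not be promised unless admission and discharge dates are collected, which the documents do not describe.

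The downside is that a crude rate treats admissions as roughly constant over time, while the columns span different ages and stages of treatment. The Part 1-restricted rate helps to check this.

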### 4.5 Motor milestones

Motor milestones assessments are made using HINE, Section 2 and WHO motor milestones (after V4 of the protocol). Each assessment is described in further detail below.

#### 4.5.1 HINE motor milestones

HINE Section 2 comprises eight tests for motor milestones: head control, sitting, voluntary grasp, ability to kick in supine position, rolling, crawling, standing, and walking.

There are 26 possible motor milestones that can be achieved using this schema (presented below). A subject whose results all appear in the first column (unable to maintain head upright, cannot sit, no grasp, etc.) has not achieved any motor milestone. A subject whose results all appear in the second column (head wobbles, sits with support at hips, uses the whole hand for a voluntary grasp, etc.) has achieved 8 motor milestones. A subject whose results all appear in the third column (head maintained upright all the time, props when sitting, index finger and thumb but immature grasp, etc.) has achieved 16 motor milestones.

*Attainment of motor milestones assessed by Section 2 of the Hammersmith Infant Neurological Examination (HINE)*

For the integrated analysis, the HINE motor milestones analyses will be presented by windowed analysis visits (see section 4.1).

The definition of a motor milestone responder is based upon the motor milestones categories in Section 2 of the HINE, with the exclusion of voluntary grasp as follows:

- Subject demonstrates at least a 2-point increase in the category of ability to kick or increase to the maximal score on that category (touching toes), or a 1-point increase in the motor milestones category of head control, rolling, sitting, crawling, standing, or walking AND
- Among the motor milestone categories, with the exclusion of voluntary grasp, there are more categories where there is improvement, as defined in (i) below, than there are categories where there is worsening (as defined below).
- Subjects who die or withdraw from the study on or prior to the visit will be counted as non-responders and will be included in the denominator

Improvement in motor milestones is defined as a 2-point increase in the total motor milestones score, where voluntary grasp is excluded. For example, (i) a 1-point increase in head control and a 1-point increase in rolling is considered a response, (ii) a 2-point increase in rolling is considered a response, (iii) a 2-point increase in rolling with a 1-point decrease in head control is considered a non-response. Worsening is defined as at least a 2-point decrease or a decrease to the lowest possible score of no kicking. For the other 6 categories, worsening is defined as at least 1-point decrease.

To illustrate this responder definition, examples are provided below. In these examples, it is assumed that there are no changes in motor milestone categories other than those stated.

- A subject with a 2-point increase of ability to kick, a 1-point increase in rolling, and a 1-point decrease in head control is a responder.
- A subject with a 1-point increase of ability to kick from “touches legs” to “touches toes” is a responder.
- A subject with a 1-point increase of head control and a 1-point decrease rolling is a non-responder.
- A subject with a 1-point increase of rolling and a 2-point decrease in ability to kick is a non-responder.
- A subject with a 1-point increase of rolling and a 1-point decrease of ability to kick from “upward vertically” to “kicks horizontal, legs do not lift” is a responder.
- A subject with a 1-point increase of rolling and a 1-point decrease of ability to kick from “kicks horizontal, legs do not lift” to “no kicking” is a non-responder.
- A subject with a 2-point increase of voluntary grasp is a non-responder.
- A subject with a 1-point increase of rolling and a 2-point decrease of voluntary grasp is a responder.

The response will be conducted on data from each visit and windowed visit separately for Part 2 and integrated analysis respectively (see section 4.1 for details about the windowing).

*Additional presentations of HINE motor milestones*

- The above responder analysis will be repeated for the subjects that are responder at last available assessment. For those subjects that are responders, the analysis visits when first respond occurred will be also displayed.
- The proportion of subjects who have achieved the follow milestones:
  - Full head control,
  - Stable sit or pivots,
  - Stand unaided,
  - Walk independently
 will be presented by visit and at the last available assessment (for the integrated analysis)
- The proportion of subjects who have achieved individual milestones will be presented by visit.

The shift from baseline to last available assessment (for the integrated analysis).

- The total motor milestones score achieved over time will be presented (for Part 2 only and the integrated analysis) .

- The change from baseline over time will be presented and a plot of both total and change from baseline will be presented (for Part 2 only and the integrated analysis) .

The analysis of motor milestones responders and summaries of total motor milestones score will also be conducted by age of SMA onset ( $\leq 6$  months,  $>6$  months).

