7. STUDY DESIGN

7.1. Study Overview

This is a Phase 2 multicenter study conducted in 2 parts. The study was originally designed as a randomized, double-blind, sham-procedure controlled study to assess the safety and tolerability and explore the efficacy of intrathecally administered Nusinersen up to approximately 14 months (from the first dose until End of Part 1 Evaluation). Based on emergent data from the Nusinersen clinical development program, the Sponsor may decide to terminate Part 1 early, and all subjects may then be offered the opportunity to be unblinded and transition to Part 2 prior to completion of all Part 1 evaluations. Part 2 is an OLE phase that will assess long-term safety and tolerability and explore the efficacy of intrathecally administered Nusinersen for approximately 24 additional months. In Part 1 of the study, up to 21 subjects will be randomized in a ratio of 2:1 to receive Nusinersen by intrathecal LP injection (n = 14) or to a sham procedure-control (n = 7). Randomization will be stratified based on age at onset of clinical signs and symptoms consistent with SMA: >6 months versus ≤6 months. In Part 2 of the study, all subjects who participated in Part 1, who completed their End of Part 1 Evaluation assessments, and who elected to enroll in Part 2 will receive Nusinersen by intrathecal injection.

Subjects who withdraw early from Part 1 will be encouraged to complete the End of Part 1 Evaluation assessments at the time of withdrawal. Subjects who withdraw early from Part 2 will be encouraged to complete the Part 2 Early Termination Evaluation assessments at the time of withdrawal.

See Section 4.1 for a schematic of the study design.

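### SAP 4.5.1 defines HINE improvement on the total score, which contradicts its own category-based responder rule and misclassifies three of its eight worked examples

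*SAP*

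**What the plan says.** SAP 4.5.1 bases the responder definition on the HINE Section 2 categories without voluntary grasp. It has two conditions that must both hold.

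- **Condition 1, a qualifying gain.** For kicking: "Subject demonstrates at least a 2-point increase in the category of ability to kick or increase to the maximal score on that category". For the rest: "a 1-point increase in the motor milestones category of head control, rolling, sitting, crawling, standing, or walking".
- **Condition 2, a count.** The subject qualifies only if "there are more categories where there is improvement, as defined in (i) below, than there are categories where there is worsening".

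The text that follows then states: "Improvement in motor milestones is defined as a 2-point increase in the total motor milestones score, where voluntary grasp is excluded". Three in-line examples, numbered (i) to (iii), come straight after. Worsening is defined by category: "Worsening is defined as at least a 2-point decrease or a decrease to the lowest possible score of no kicking", which must refer to kicking, and a loss of at least 1 point in each of the other six categories. Eight bulleted examples follow, offered as illustrations of the responder definition and assuming no other changes.

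The response is analysed by visit in Part 2 and by windowed visit in the integrated data. It is repeated at the last available assessment. In addition, "The analysis of motor milestones responders and summaries of total motor milestones score will also be conducted by age of SMA onset".

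**The concern.** Condition 2 needs a yes/no answer for each category. The definition it leads to gives one answer per subject, so the two sides of the count are in different units: worsening by category, improvement by total. The cross-reference does not help, because item (i) is an example and not a definition.

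If a programmer implements the total-score sentence and a validator implements the category rule, both can say they followed the SAP and still classify the same child differently. The responder proportions by visit, at last assessment, by first visit of response and by onset stratum would all depend on which reading was coded. With groups this small, a few discordant subjects would be visible in the tables.

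**Working it through.** **Inputs.** The two conditions, the improvement sentence, the worsening definitions, the eight bullets and the in-line examples (i) to (iii) are all from SAP 4.5.1. The planned group sizes, 14 nusinersen and 7 sham, are from Protocol 7.1.

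**Definitions.** Drop voluntary grasp. For each subject:

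- T = sum of the changes over the seven remaining categories.
- I = number of categories improved (kicking up by at least 2 or to its maximum; any other category up by at least 1).
- W = number of categories worsened (kicking down by at least 2 or to its lowest score; any other category down by at least 1).
- Category rule: responder if I ≥ 1 and I > W.
- Total rule: responder if T ≥ 2.

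**The SAP's own labels** (R = responder, N = non-responder):

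| Example | Change | T | I | W | SAP label | Category rule | Total rule |
|---|---|---|---|---|---|---|---|
| 1 | kick +2, rolling +1, head −1 | +2 | 2 | 1 | R | R | R |
| 2 | kick +1, reaching its maximum | +1 | 1 | 0 | R | R | **N** |
| 3 | head +1, rolling −1 | 0 | 1 | 1 | N | N | N |
| 4 | rolling +1, kick −2 | −1 | 1 | 1 | N | N | N |
| 5 | rolling +1, kick −1, not to lowest | 0 | 1 | 0 | R | R | **N** |
| 6 | rolling +1, kick −1, to lowest | 0 | 1 | 1 | N | N | N |
| 7 | grasp +2 only | 0 | 0 | 0 | N | N | N |
| 8 | rolling +1, grasp −2 | +1 | 1 | 0 | R | R | **N** |
| (i) | head +1, rolling +1 | +2 | 2 | 0 | R | R | R |
| (ii) | rolling +2 | +2 | 1 | 0 | R | R | R |
| (iii) | rolling +2, head −1 | +1 | 1 | 1 | N | N | N |

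- Category rule: 8 of 8 bullets and 3 of 3 in-line examples match.
- Total rule: 5 of 8 bullets match; examples 2, 5 and 8 fail. Example 8 reads "A subject with a 1-point increase of rolling and a 2-point decrease of voluntary grasp is a responder", yet its total rises by only 1.
- Other readings do not rescue the sentence. Requiring T to equal exactly 2, adding condition 1 to the total rule, or requiring both full rules each fails the same three. Reading improvement as at least 2 points within a category fails four bullets (1, 2, 5, 8) and in-line example (i).
- The in-line examples agree with both rules, so they give a programmer no warning.

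**Direction of disagreement.**

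- A lone +1 in any of the six non-kicking categories has T = 1, below 2: responder by category, non-responder by total.
- A constructed case goes the other way. Rolling +2, sitting +2, head −1, standing −1 gives T = 2 + 2 − 1 − 1 = +2, but I = 2 and W = 2: non-responder by category, responder by total. Gains of 2 are attainable, since SAP 4.5.1 credits 16 milestones to a child in the third column on all eight tests, or 16/8 = 2 per test.

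**Weight of one subject.** 1/7 = 14.3 points; 1/14 = 7.1 points; 1/21 = 4.8 points. These use planned numbers. SAP 4.1 denominators vary by visit, so a single subject can weigh more.

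**The case against.** The best defence is that the SAP largely corrects itself. It opens by tying response to categories, condition 1 already gives the category thresholds, and anyone testing code against the eight bullets would hit the mismatch at the second one. That stands as evidence of intent, and it is why the fix needs no guesswork. It does not excuse the sentence, which is the stated definition, while the bullets are offered only as illustrations.

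The sentence could be read as a separate total-score endpoint. The text does not support that. It is the only definition of improvement after the forward reference, its in-line examples are scored as response or non-response, and the SAP summarises the total score separately.

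Some limits on the impact do stand:

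- Disagreement in both directions arises only if the total rule replaces the category count. If both rules must be met, the error is one way, towards fewer responders.
- The per-subject weights apply to any proportion and are not an estimate of this defect's effect. The 1/21 figure could arise only in the Part 2 total column, because SAP Section 2 lists no total group for the integrated efficacy displays.
- The by-visit response is specified for both Part 2 and the integrated data. The text does not say whether the last-assessment and onset-age versions cover both.
- The endpoint is exploratory, no hypothesis test is specified for it, and the primary safety and secondary PK results do not depend on it.

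**Conclusion.** The concern holds. The total-score sentence cannot operate inside the category rule that relies on it, and it gives the wrong classification for 3 of the SAP's 8 worked examples. The category definition gives the right one for all 11 labelled cases. This assumes that the first worsening sentence refers to kicking, which its wording implies.

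The net effect on the responder proportion is unknown, because neither document gives a distribution of HINE changes. The point deserves correction but is not critical: it affects how an exploratory endpoint is classified and leaves the trial's main conclusions untouched.

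**What to change.** In SAP 4.5.1, remove the total-score sentence and the reference to item (i), and state the rule once:

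- *Improved category:* ability to kick rises by 2 or more points or reaches its top score; any of head control, rolling, sitting, crawling, standing or walking rises by 1 or more.
- *Worsened category:* ability to kick falls by 2 or more points or drops to its lowest score; any of the other six falls by 1 or more.
- *Responder:* at least one improved category, and more improved than worsened categories. Voluntary grasp is ignored throughout.

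This text should replace the existing responder conditions and worsening sentences so that two versions do not sit side by side. Move in-line examples (i) to (iii) into the list of worked examples, where they still hold. Keep the existing treatment of deaths and withdrawals as non-responders. If a 2-point rise in the total is also of interest, name it as a separate sensitivity analysis.

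The cost is one paragraph of SAP text, plus a check that any existing program returns the 11 labels above. No new data and no change to assessments are needed.
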